2.2.6 Sensitivity efficacy analyses (Phase 2 only)

Parameters of Response by RECIST v1.1 in the safety population:

- ORR (RECIST v 1.1, safety population)
- DoR (RECIST v1.1, safety population)

2.3 Study Design

This is a Phase 1b-2 study. The study will include 2 parts.

Phase 1b dose-escalation of APX005M:

[figure not shown]
- Up to 4 dose levels of APX005M administered IV every 21 days
- In combination with nivolumab 360 mg IV every 21 days
- Participants with inNSCLC or PD1-MM

Phase 2 dose-expansion (Simon optimal 2-stage design):

- The RP2D dose of APX005M administered IV every 21 days in combination with nivolumab 360 mg IV
- 3 cohorts
 - Cohort 1: Participants with inNSCLC
 - Cohort 2: Participants with PD1-MM
 - Cohort 3: Participants with PD1-NSCLC
 - Group A: Participants with PD1-NSCLC with best response of progressive disease or with stable disease < 16 weeks while on previous PD-1/PD-L1 containing regimen
 - Group B: Participants with PD1-NSCLC with tumor response or with stable disease ≥ 16 weeks while on previous PD-1/PD-L1 containing regimen

Participants will be evaluated for tumor response approximately every 8 weeks following the first dose of investigational product. An ORR of at least 22% (6 out of 24 response evaluable participants) in the inNSCLC cohort and 5% (1 out of 12 response evaluable participants) in the PD1-MM cohort or PD1-NSCLC (Group A or B) is required in Stage 1 for that cohort to proceed to Stage 2. Enrollment may continue into Stage 2 while the planned number of participants for Stage 1 are followed for efficacy.

Figure 1 APX005M-002 Study Design

2.3.1 Eligibility and Randomization

This is an open-label study, and there is no randomization or blinding needed.

2.3.2 Eligibility Criteria

2.3.2.1 Phase-Specific Criteria

Phase 1b: Participants that meet eligibility criteria for Phase 2 Cohorts 1 or 2 and all the general eligibility criteria.

Phase 2 Cohort 1: Histologically or cytologically confirmed, immunotherapy naïve, metastatic or locally advanced non-small cell lung cancer not amenable to curative treatment. Participants may be treatment naïve or could have received one prior platinum-based chemotherapy for non-small cell lung cancer for any indication (adjuvant, part of combined modality therapy or for metastatic disease) within the past 3 years. Participants with no or unknown activating mutation (e.g., EGFR, ALK, ROS) are eligible for this study. Participants with a documented activating mutation (e.g., EGFR, ALK, ROS) amenable to tyrosine kinase inhibitor therapy, must also have received the appropriate therapy and progressed.

Phase 2 Cohort 2: Participants with histologically or cytologically confirmed unresectable or metastatic melanoma that had confirmed progressive disease during treatment with anti-PD-1/PD-L1 therapy. Participants with BRAF wild type or unknown status must have received only anti-PD-1/PD-L1 therapy. Participants with BRAF activating mutation could have also received a BRAF inhibitor and/or MEK inhibitor regimen prior to anti-PD-1/PD-L1 therapy.

Confirmed PD during treatment with anti-PD-1/PD-L1 therapy should be documented by 2 consecutive tumor assessments at least 4 weeks apart (the second scan may be used as the baseline scan for this study if it was performed within the 21 days prior Cycle 1 Day 1). Participants should start study treatment no later than 8 weeks following the last dose of anti-PD-1/PD-L1 therapy.

Participants with ocular melanoma are excluded.

Phase 2 Cohort 3: Participants with histologically or cytologically confirmed, metastatic or locally advanced NSCLC not amenable to curative treatment. Participants must have disease progression on an immediately preceding PD-1/PD-L1 containing regimen. Participants could have received no more than one platinum containing regimen, or if participants have a documented activating mutation (e.g. EGFR, ALK, ROS) amenable to tyrosine kinase inhibitor therapy, must also have received the appropriate therapy and progressed before the PD-1/PD-L1 containing regimen.

Based on response to previous PD-1/PD-L1 containing regimen, participants will be enrolled in one of the following groups:

- Group A: Participants with best response of progressive disease or with stable disease < 16 weeks
- Group B: Participants with tumor response or with stable disease ≥16 weeks.

If possible, confirmed PD during treatment with anti-PD-1/PD-L1 therapy should be documented by 2 consecutive tumor assessments at least 4 weeks apart (the second scan may be used as the baseline scan for this study if it was performed within the 21 days prior Cycle 1 Day 1). Participants should start study treatment no later than 8 weeks following the last dose of anti-PD-1/PD-L1 containing regimen.

2.3.2.2 General Inclusion Criteria

1. Subjects willing and able to provide written informed consent for this study
2. Male or female ≥18 years old at time of consent
3. Measurable disease by RECIST criteria v1.1
4. ECOG performance status of 0 or 1
5. Resolution of prior treatment-related toxicities to Grade 1 (check the protocol for some exceptions)
6. Adequate organ function within 14 days of first dose of investigational product (check protocol for appropriate parameters guidelines)
7. Women of childbearing potential (WOCBP) must have negative pregnancy test (check protocol for more details)
8. WOCBP and males who are sexually active with WOCBP must agree to follow instructions for method(s) of contraception (check protocol for more details)
9. Available archived or fresh tumor tissue sample for PD-L1 and other biomarker analysis
10. For subjects that consent to collection of tumor biopsies at study entry and before the first scheduled tumor assessment, primary or metastatic tumor that can be safely biopsied. A minimum of 24 subjects (6 subjects with each cohort/group) must consent to fresh core biopsies.

2.3.2.3 General Exclusion Criteria

1. Previous exposure to any immunomodulatory agents (check exceptions in the protocol)
2. Second malignancy (solid or hematologic) within the past 3 years (check exceptions in the protocol)
3. Active, known, clinically serious infections (≥ Grade 2 according to NCI-CTCAE v4.03) within the 14 days prior to first dose of investigational product
4. Use of systemic corticosteroids or other systemic immunosuppressive drugs within the 28 days prior to first dose of investigational product (except inhaled corticosteroids); the use of physiologic doses of corticosteroids may be approved after consultation with the Apexigen Medical Monitor (or designee)

5. Major surgery within 4 weeks of first dose of investigational product
6. Concurrent treatment with any anti-cancer agent, except for hormonal therapy and palliative radiation as clinically indicated unless approved by the Medical Monitor
7. History of allogeneic bone marrow transplantation
8. Uncontrolled diabetes or hypertension
9. Active autoimmune disease that has required systemic treatment in past 2 years (i.e. with use of disease modifying agents, corticosteroids or immunosuppressive drugs). Subjects with type I diabetes mellitus, hypothyroidism only requiring hormone replacement, skin disorders (such as vitiligo, psoriasis, or alopecia) not requiring systemic treatment, or conditions not expected to recur in the absence of an external trigger are permitted to enroll.
10. History of (non-infectious) pneumonitis that required corticosteroids or current pneumonitis
11. History of interstitial lung disease
12. History of life-threatening toxicity related to prior anti-PD-1/PD-L1 treatment for subjects with metastatic melanoma except those that are unlikely to re-occur with standard countermeasures (e.g. hormone replacement after adrenal crisis)
13. History of sensitivity or allergy to mAbs or IgG
14. Congestive heart failure (New York Heart Association Class III to IV), symptomatic ischemia, conduction abnormalities uncontrolled by conventional intervention, or myocardial infarction within 6 months prior to the first dose of investigational product
15. History of any thromboembolic event within 3 months prior to first dose of investigational product or an active coagulopathy
16. Known active central nervous system (CNS) metastases and/or carcinomatous meningitis. Subjects with untreated brain metastases ≤ 3 mm that are asymptomatic, do not have significant edema, cause shift, require steroids or anti-seizure medications are eligible after discussion with the Medical Monitor. Lesions of any size in posterior fossa are excluded. Subjects with previously treated brain metastases may participate provided they are stable after treatment (without evidence of progression by imaging for at least 4 weeks prior to the first dose of trial treatment and any neurologic symptoms have returned to baseline), have no evidence of new or enlarging brain metastases, and are not using corticosteroids for at least 7 days prior to trial treatment. This exception does not include carcinomatous meningitis which is excluded regardless of clinical stability
17. Known human immunodeficiency virus (HIV), hepatitis B or hepatitis C infection
18. Has received a live-virus vaccination within 30 days of the first dose of investigational product. Seasonal flu vaccines that do not contain live virus are permitted
19. Pregnant, breastfeeding, or unwilling to practice birth control during participation in the study
20. Any clinically significant psychiatric, social, or medical condition that, in the opinion of the Investigator, could increase subject's risk, interfere with protocol adherence, or affect a subject's ability to give informed consent.

2.3.3 Withdrawals

Participants MUST discontinue receiving investigational product for any of the following reasons:

- Disease progression by RECIST 1.1, or disease progression following treatment beyond progression
- Death
- Toxicity requiring discontinuation of both investigational products as outlined in the dose modification guidelines
- Failure to recover from a disease or treatment-related AE to baseline or \leq Grade 1 within 12 weeks of last dose of investigational product (except Grade 2 alopecia and Grade 2 fatigue), unless the participant is benefiting from therapy and after discussion with and approval by Apexigen Medical Monitor (or designee)
- Failure to recover within 4 weeks of last dose of investigational product if AE is related to infusion reaction/cytokine release
- Inability to reduce corticosteroid to 10 mg or less of prednisone or equivalent per day within 12 weeks of last dose of investigational product and after discussion with and approval by Apexigen Medical Monitor (or designee)
- Participant's decision to withdraw for any reason from study treatment (participant withdraws consent)
- Pregnancy
- Any clinical AE, laboratory abnormality or coincident illness which, in the opinion of the Investigator, indicates that continued participation in the study is not in the best interest of the participant
- Requirement for alternative therapy
- Noncompliance with study procedures, including use of prohibited medications
- Participant is lost to follow-up
- Loss of ability to freely provide consent through imprisonment or involuntarily incarceration for treatment of either a psychiatric or physical (e.g., infectious disease) illness
- Study termination by Apexigen

The primary reason for treatment discontinuation will be documented in the eCRF.

Apexigen (or designee) must be notified within 24 hours if a participant is withdrawn from treatment.

Participants who are withdrawn from both investigational products will enter the follow-up period unless treatment discontinuation is due to any of the following:

- Participant death
- Withdrawal of consent for all study procedures
- Initiation of any anticancer therapy
- Participant is lost to follow-up
- Study termination by Apexigen

For all participants receiving investigational products, the subsequent anticancer therapy will be documented. Once this information is collected, a participant is considered off-study.

2.3.4 Study treatment

In this study, the investigational products are APX005M and nivolumab.

Nivolumab is administered on Day 1 of each 3-week treatment cycle as a dose of 360 mg using a 30-minute IV infusion.

APX005M is administered on Day 1 of each 3-week treatment cycle approximately 30 minutes following nivolumab using a 60-minute IV infusion. Up to 4 dose levels of APX005M could be used in Phase 1b and the RP2D will be used for Phase 2, which will be determined during the Phase 1b of this study (between 0.03 and 0.3 mg/kg).

2.3.5 Replacement of Patients

- For Phase 1b of the study, all participants that are not DLT-evaluable will be replaced for the purpose of establishing MTD.
- For Phase 2 of the study, participants will be evaluated for tumor response approximately every 8 weeks following the first dose of investigational product. Participants that are non-evaluable for tumor response will be replaced.

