Subjects will be evaluated for tumor response approximately every 8 weeks following the first dose of investigational product. Subjects that are non-evaluable for tumor response (see definition in [Section 7.2](#)) will be replaced. An ORR [complete response (CR) + partial response (PR)] of at least 22% (6 confirmed out of 24 response evaluable subjects) in the inNSCLC cohort and 5% (1 confirmed out of 12 response evaluable subjects) in the PD1-MM cohort or PD1-NSCLC (Group A or B) is required in Stage 1 for that cohort to proceed to Stage 2. Enrollment may continue into Stage 2 while the planned number of subjects for Stage 1 are followed for efficacy.

In Stage 2, an additional 21 subjects will be enrolled in Cohort 1 (inNSCLC) and an additional 25 subjects will be enrolled in each of Cohort 2 (PD1-MM) and Cohort 3 (PD1-NSCLC) Group A and B. The study schema is presented in [Figure 1](#).

Figure 1: APX005M-002 Study Design

A minimum of 6 subjects per cohort/group who have a primary or metastatic lesion that can be biopsied without interfering with subsequent tumor assessments and who consent to collection of paired tumor biopsies for tumor biomarkers should be enrolled during Phase 1b and Phase 2.

At any time during the study, enrollment will be suspended pending safety review if any of the following events occur since last safety review:

- ≥1 Grade 5 suspected adverse reaction (SAR) (for definition see [Section 6.1.2](#))
- ≥2 Grade 4 infusion reaction/ cytokine release syndrome

- ≥ 2 Grade ≥ 3 immune related AEs in more than 1 subject

Enrollment will resume following assessment by the Apexigen Medical Monitor, contract research organization Medical Monitor and lead Investigator.

For subjects that require confirmation of PD while on treatment with anti-PD-1/PD-L1 therapy, any of the following criteria must be met:

- ≥ 5 mm further increase in sum of measures of target lesion
- ≥ 5 mm further increase in sum of measures of new lesion
- further increase in the size of non-target lesion(s)
- new non-target lesions
- appearance of new lesion(s) when none have previously been recorded
- increase in the number of new lesions
- all of the following
 - maintain $> 20\%$ increase in target lesion burden at confirmed PD scan relative to nadir (as per RECIST1.1)
 - target lesion burden at confirmatory PD scan greater than 90% of target lesion burden at unconfirmed PD (initial PD) scan (to account for intra-subject reader variability)

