7.1 Sample Size Determination

This is a Phase 1b-2, study. The sample size for the Phase 1b dose-escalation cannot be precisely estimated but depends upon the observed toxicities. Cohorts of 3 to 6 subjects will be treated at each DL during dose escalation portion of the study. It is anticipated that approximately 18 subjects will be treated in this portion of the study depending on the actual rate of DLTs.

Sample size for Phase 2 is calculated using the Simon optimal 2-stage design [32]:

- **Cohort 1 (inNSCLC):** Assuming a false positive rate (α) of 0.1 (one-sided), a false negative rate (β) of 0.1, a response probability of poor drug (P0) of 22% and a response probability of good drug (P1) of 40%, first stage sample size (n1) is 24 and the maximum sample size (n) is 45 response evaluable subjects. In the first stage, if there are 5 or less responses in 24 subjects, the enrollment in this cohort will be stopped. Otherwise, if 6 or more responses are observed, 21 additional subjects will be accrued in Stage 2 for total of 45. Enrollment may continue into Stage 2 while the planned number of subjects for Stage 1 are followed for efficacy. By the end of Stage 2, if 13 or less responses are observed in 45 subjects, then no further investigation is warranted. If 14 or more responses are observed, the null hypothesis will be rejected and true RR is 40%.

The sample size of 45 subjects, provides 97% power to statistically test the null hypothesis of historical 6-month PFS rate (PFSR) of 60% (estimated for pembrolizumab in Keynote-024 [33]) versus the alternative hypothesis of 6-month PFSR rate of 80%. This calculation assumes exponential PFS, 1-sided 5% type I error rate, enrollment of subjects for 8 months with 6 months of follow-up prior to conducting the final analysis.

- Cohort 2 (PD1-MM): Assuming α of 0.1 (one-sided), β of 0.1, P0 5% and P1 of 20%, n1 is 12 and n is 37 response evaluable subjects. In the first stage, if there are no responses in 12 subjects, the enrollment in this cohort will be stopped. Otherwise, if 1 or more responses are observed, 25 additional subjects will be accrued in Stage 2 for total of 37. Enrollment may continue into Stage 2 while the planned number of subjects for Stage 1 are followed for efficacy. By the end of Stage 2, if 3 or less responses are observed in 37 subjects, then no further investigation is warranted. If 4 or more responses are observed, the null hypothesis will be rejected and true RR is 20%.

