7.2 Populations for Analyses

All subjects receiving both investigational products will be included in the safety population.

Subjects evaluable for DLT are defined as those who meet study eligibility criteria, receive the entire planned dose of APX005M and nivolumab and have follow-up for at least 21 days (i.e., subject does not come off study for reasons other than toxicity).

Subjects evaluable for efficacy (tumor response) are defined as those who meet study eligibility criteria and have at least one on treatment (post baseline) tumor assessment.

Subjects evaluable for PK are defined as those who have adequate APX005M serum concentration-versus-time data to allow proper estimation of PK parameters.

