4.2 Efficacy Endpoint

- The Progression-Free Survival (PFS) is defined as the time from first dose of investigational product to the earlier of PD (by RECIST 1.1 and iRECIST) or death due to any cause. PFS will be calculated as time in months between (first date of PD or death due to any cause – date of first dose).

- For participants with no baseline assessment, PFS will be censored on the date of first dose.
- For alive participants with no post baseline tumor assessment will be censored on the date of first dose however they will be considered an event in case of record end of treatment by clinical progression within eight weeks of first treatment dose (before the first tumor assessment schedule)
- For participants who have at least 1 post baseline tumor assessment, if they do not have PD or do not die, PFS will be censored on the date of last tumor assessment documenting the absence of PD.

PFS will be summarized using the Kaplan Meier method; the median event time (if appropriate) and two-sided 90% CI for the median will be provided (Brookmeyer and Crowley method). PFS by RECIST 1.1 and by iRECIST will be summarized by dose level and overall in each tumor type for Phase 1b and by cohort for Phase 2 (including participants treated at RP2D in Phase 1b) in 2 separate tables. A graph of the Kaplan Meier curve will be presented for Phase 2 (including participants treated at RP2D in Phase 1b).

- The Best Overall Response (BOR) is defined as the best response presented according to RECIST v1.1 from the inclusion in the study to progressive disease (PD).
- The Objective Response Rate (ORR) is defined as the incidence of patients who show as best overall response a complete response (CR) or partial response (PR). The ORR can be calculated based on two tumor assessment methods, RECIST 1.1 and iRECIST.

The point estimate of the ORR will be presented along with exact two-sided 90% confidence interval (CI) using the exact method (Clopper-Pearson).

- The Duration of Response (DoR) is defined as the time in months from the first evidence of confirmed PR or better to disease progression or death due to any cause, whichever occurs earlier (by RECIST 1.1 and iRECIST). DoR will be calculated for the participants with a response of PR or better. If participants do not have PD or do not die, DoR will be censored on the date of last tumor assessment documenting the absence of PD.

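### Treated subjects who die or progress clinically before the first scan are replaced and left out of the primary ORR and both Simon decisions; if P0 is an all-treated rate, the false-positive rate exceeds 0.10

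*SAP*

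**What the plan says.** Protocol 7.2 defines subjects evaluable for tumor response as "those who meet study eligibility criteria and have at least one on treatment (post baseline) tumor assessment"; SAP 3.4 agrees. Neither makes an exception for death, clinical progression or toxicity before the scan. Tumor assessments are every 8 weeks ± 1 week (Protocol 5.1 and 5.5).

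Protocol 2.2 states that "Subjects that are non-evaluable for tumor response" are to be replaced, and SAP 2.3.5 repeats it: "Participants that are non-evaluable for tumor response will be replaced". The Simon sizes count the same group. For Cohort 1, Protocol 7.1 gives "first stage sample size (n1) is 24 and the maximum sample size (n) is 45 response evaluable subjects"; for Cohorts 2, 3A and 3B the sizes are 12 and 37, also response evaluable. The Stage 1 gates in Protocol 2.2 and SAP 2.3 use that denominator, and SAP 5.4.2 runs the efficacy analysis in the Efficacy Population.

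Three other provisions bear on the point:
- SAP 2.2.6 lists a sensitivity analysis, "ORR (RECIST v 1.1, safety population"), with no decision rule attached.
- For PFS, SAP 4.2 says of living subjects with no post-baseline scan that "they will be considered an event in case of record end of treatment by clinical progression within eight weeks of first treatment dose".
- Protocol 5.1 and 5.2.4 ask that subjects who stop treatment without documented progression continue to be imaged on the same schedule.

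**The concern.** Death or clinical progression before week 8 is a failure of treatment, not data missing by chance. The replacement rule removes that failure and puts in its place a subject selected for having reached a scan. The error always runs in the favourable direction, and it affects the primary estimate, the Stage 1 gate and the final cut-off alike. The safety-population ORR lets a reader see the difference afterwards but changes no decision. At stake is whether a regimen no better than the null goes forward more often than the design allows.

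**Working it through.** **Inputs.** Protocol 7.1: "Assuming a false positive rate (α) of 0.1 (one-sided), a false negative rate (β) of 0.1". Cohort 1 has P0 22%, P1 40%, stop at 5 or fewer of 24, fail at 13 or fewer of 45. Cohorts 2, 3A and 3B have P0 5%, P1 20%, stop at 0 of 12, fail at 3 or fewer of 37. The fraction f of treated subjects lost before a scan is given nowhere, so it is an assumption, shown over a range.

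**Formula.** With first-stage limit r1 of n1 and final limit r of n,

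P(reject | p) = Σ over x = r1+1 … n1 of P[Bin(n1, p) = x] × P[Bin(n − n1, p) ≥ r + 1 − x].

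**The plan's own design.** A full search for the Simon optimal design returns exactly 5/24, 13/45 and 0/12, 3/37. Exact alpha and power are 0.0937 and 0.900 (Cohort 1) and 0.0935 and 0.902 (the others). The Simon arithmetic is right; the question is the denominator.

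**Effect of replacement.** Suppose P0 is the response rate among all treated subjects. A lost subject cannot be a responder, so the null rate among evaluable subjects is P0/(1 − f). At f = 10% this is 0.22/0.90 = 0.2444 and 0.05/0.90 = 0.0556. Applying the same rules at these rates:

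| f | Cohort 1: null rate | alpha | passes Stage 1 | Cohorts 2/3A/3B: null rate | alpha | passes Stage 1 |
|---|---|---|---|---|---|---|
| 0 | 0.2200 | 0.094 | 0.439 | 0.0500 | 0.093 | 0.460 |
| 5% | 0.2316 | 0.130 | 0.493 | 0.0526 | 0.108 | 0.477 |
| 10% | 0.2444 | 0.179 | 0.553 | 0.0556 | 0.124 | 0.496 |
| 15% | 0.2588 | 0.244 | 0.616 | 0.0588 | 0.144 | 0.517 |

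Alpha reaches 0.10 at f = 0.98% in Cohort 1 and 2.4% in the others. A loss share of one in 46 gives 0.108 in Cohort 1; one in 38 gives 0.1005 in the others.

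**Effect on the estimate.** At f = 10%, 45 evaluable subjects mean 45/0.90 = 50 treated. The smallest passing result, 14/45 = 31.1%, is then 14/50 = 28.0% of treated subjects. For the other groups 37/0.90 is about 41, and 4/37 = 10.8% becomes 4/41 = 9.8%.

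**Plausible range of f.** Protocol 7.1 assumes exponential PFS, with a null 6-month rate of 60% in Cohort 1. Progression or death by week 8 is then 1 − 0.60^(8/26) = 14.5%. Subjects who progress or die and are also never scanned are a subset of these. Toxicity stops without a scan could add some, but values above about 15% do not fit the plan's own figures. For Cohort 2 (19%) and Cohort 3 (22%) the same formula gives 40% and 37%, so f is not tightly bounded there.

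**After the fix.** With no replacement and unscanned subjects counted as non-responders, the rules act on all treated subjects. If P0 and P1 are all-treated rates, alpha and power return to the design values whatever f is. If P1 was meant for evaluable subjects, the rate becomes P1(1 − f). Cohort 1 power is then 0.846 at f = 5% and 0.775 at f = 10%; in the others it is 0.857 at f = 10%.

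**The case against.** The best defence is that the design is coherent on its own terms. Sample sizes, gates, replacement rule and efficacy population all refer to response-evaluable subjects, and for that population alpha is 0.094 and 0.093. A reader might infer from the table that the trial's false-positive rate simply fails. The documents do not support that: they give no source for P0 on ORR, so it cannot be shown to be an all-treated rate. This part of the defence stands, and the loss of alpha is conditional. What remains is that a test valid only for subjects who reached a scan does not answer the question for those who start treatment.

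Three other stronger readings also go too far.
- *Every early toxicity stop is lost.* Off-treatment imaging is requested, so many would be scanned at week 8. Whether that scan counts turns on the words *on treatment* in the definition, which is an ambiguity to settle. Deaths raise no such doubt.
- *The SAP plainly counts the same subject as a PFS failure.* SAP 4.2 has such a rule, but SAP 5.4.2 assigns the efficacy analysis, PFS included, to a population that excludes unscanned subjects. Read literally, the rule never reaches them. That is an internal conflict, not proof of a settled double standard.
- *Alpha in Cohort 1 could be about 0.33.* That needs f = 20%, which the cohort's planning values do not allow under the null.

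The safety-population ORR does soften the reporting problem. It enters no gate or test, however, and it covers only subjects who received both products.

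**Conclusion.** The selection follows directly from the text: early deaths and clinical progressions leave the primary ORR and both Simon decisions, and the ORR among treated subjects is overstated by a factor 1/(1 − f). The effect on alpha rests on two assumptions: that P0 is an all-treated rate, and the value of f. Over f = 5–10% it is material in Cohort 1 and modest in Cohorts 2, 3A and 3B. This should be fixed, but it does not invalidate the design: evaluable-only analysis was prespecified consistently in both documents, and an all-treated ORR is already planned.

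**What to change.** - In Protocol 2.2 and 7.2 and SAP 2.3.5 and 3.4, count an eligible treated subject with no post-baseline scan because of death, clinical progression or treatment-related toxicity as a non-responder in the primary ORR and both Simon decisions. Do not replace that subject.
- SAP 5.4.8 expected the last enrolment in Q2 2020 and SAP 7 cites a February 2021 file, so replacements may already have been enrolled. If so, apply the rule at analysis: make the all-treated ORR primary and keep the evaluable-only ORR as sensitivity. State how the cut-offs for 45 and 37 are to be read if more subjects were treated.
- State that a scan obtained after stopping treatment without progression counts as a post-baseline assessment.
- Align the PFS population in SAP 5.4.2 with the rule in SAP 4.2, so that unscanned subjects are included in PFS.
- State whether P0 and P1 refer to treated or evaluable subjects.

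The work is wording and programming, since the primary reason for stopping treatment is already recorded on the eCRF. The reported ORR will be slightly lower, and if P1 was meant for evaluable subjects the power loss shown above should be stated openly. SAP 5.3 also removes major deviators from the efficacy population; that is a separate selection which this change does not address.
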